Our recent investigations of the proteome of three patients with significant hyperfibrinolysis, two who had ALI but survived and one who developed ARDS and did not, were compared to healthy controls of the same gender. The hyperfibrinolytic state of these injured patients was confirmed by thrombelastograms (TEG) prior to blood component resuscitation (results not shown). The proteins that significantly increase in the patient plasma vs. normal males include: actin (15-28-fold), a cytoplasmic protein that has been implicated in ALI when free in the circulation, von Willebrand Factor (15-24-fold), a necessary coagulation factor, α -enolase (10-28-fold)⁵⁹ a lyase with protease activity, perioxiredoxins 2 & 6 (7-14-fold), proteins which are atypical phospholipases, adiponectin (8-19-fold), which is a hormone from adipocytes that is important in glucose uptake & insulin sensitivity, PPAR1/PPAR2 lipid oxidation and is а ligand. matrix metalloproteinase-9 (MMP-9) (3-5-fold) that is also known as gelatinase, which breaks down the extracellular matrix and is a sensitive indicator of leukocyte activation and, lastly, carboxypeptidase β2, also known as TAFI. Plasma contains many proteins which can oppose the actions of these proteins, including: anti-proteases (a1antitrypsin, a2-macroglobulin, and other globulins), lipid carriers (albumin), and gelsolin which solubilizes and inhibits actin induced ALI.^{57, 58, 60, 108}

1. **Hypothesis**: Experimental group patients will demonstrate earlier and larger improvement in coagulation variables compared to control patients.

2. Statistical analysis: variables will be examined for normality through the Shapiro-Wilk test and log-transformed if necessary to approximate normality. Statistical analyses will be performed by using mixed linear models (SAS Proc Mixed), with an unstructured covariance structure between the different time measures, and if needed, adjustment for potential confounders in case randomization fails to account for differences. Overall experiment error will be adjusted for the number of coagulation parameters being analyzed using the Bonferroni method. Multiple comparison adjustment within each coagulation variable temporal trend will be done using the Tukey's method.

Mixed linear modeling with SAS Proc Mixed allows for incomplete data, thus all observed points will be used in the analysis. Missing data in temporal trends will be dealt with differently depending on the reason for missing. If MAR (loss to followup, withdrawn from study), multiple imputation methods will be used, as recommended by the Panel on Handling Missing Data in Clinical Trials. However, as described in previous sections, a major reason for missing data in these cases is early death, resulting in data MNAR, for which we will use the same approach to deal with the missing data as described for the secondary endpoints.

A similar analysis will be carried out for temporal trends in Proteomic Profile, Actin and Neutrophil Elastase inhibitors.

5. Blood components transfusion in the first 12 hours postinjury

a. Packed Red Blood Cells (RBC) volume

1. **Hypothesis:** The volume of RBC transfused in the first 12 hours postinjury will be larger among control patients compared to the experimental group patients.

b. Plasma volume

- **1. Hypothesis:** The volume of plasma transfused in the first 12 hours postinjury will be larger among control patients compared to the experimental group patients.
- 2. Statistical test for a.1 and b.2: These variables are usually non-normally distributed, thus the Wilcoxon non-parametric test will be used to compare the two groups and median/interquartile range will be used to express data central tendency and dispersion. If adjustment for covariates is needed, we will follow the procedure described for continuous, not normally distributed variables. Overall experiment error will be adjusted for the number of blood transfusion parameters being analyzed using the Bonferroni method.
- c. **Time to first RBC:** This is a variable of high importance for DOD, which leads to direct application in war theater trauma.

- **1. Hypothesis:** Time to the first RBC will be longer among patients in the experimental group compared to control patients.
- 2. Statistical test: Kaplan Meyer curves will be compared using SAS PROC LIFETEST, which provides nonparametric k-sample tests based on weighted comparisons of the estimated hazard rate of the individual population under the null and alternative hypotheses. A variety of tests can be specified, of which we will use the Wilcoxon test (which places more weight on shorter survival times) and the log-rank test (which privileges longer survival times). SAS PROC LIFETEST also constructs statistics to test for association between covariates and the lifetime variable through rank tests for the association of survival time with covariates

H. Missing data prevention and treatment procedures:

We will follow the recommendations for prevention and treatment procedures outlined in the recent report by the National Research Council Panel on Handling Missing Data in Clinical Trials.⁸⁴ Missing data prevention is crucial in the primary endpoint to avoid any reduction in statistical power and the need for statistical analyses to account for the missing data. To minimize bias by missing data, research coordinators will collect data on the primary and secondary endpoints of all patients who were randomized in the field (including vital status at day 28 postinjury), including data on those patients who did not complete the protocol or were excluded for protocol violations or other reasons. Patients who withdraw from the study will be asked to allow research coordinators to collect SOC data from their medical record and, at a minimum, to provide contact information (and permission to be contacted) for verification of the primary endpoint mortality.

Based on previous trials in our institution, we predict that mortality will be missing due to loss of follow up in less than 2% of the sample. This is comparable to the loss to follow-up observed in the ROC trial (2 out 895 field-randomized patients). Several prevention procedures are in place to prevent missing data in our institution. At least two other data collection mechanisms (in addition to the COMBAT trial) will be capturing data from these patients: the Trauma Registry and the COMBAT/Trauma Activation database, which include information on the primary and secondary endpoints for COMBAT-eligible patients.

However, we are aware that avoiding missing data completely is not always possible. Thus, as in the ROC trial, we will assume that patients for whom vital status (the primary endpoint) could not be verified despite reasonable efforts to ascertain it were alive at day 28.⁶⁷ Patients lost to follow up will be fully described in terms of group assignment and covariates. Mortality data will most likely be "missing at random" (MAR). This is a reasonable assumption since patients with missing data on day 28 vital were those discharged alive before day 28 and lost to follow-up. Mortality in this group is most likely unrelated to the trial group assignment. In the unlikely event that vital status data are missing in over 5% of the sample, we will conduct a sensitivity analysis assuming

extreme case scenarios (i.e., all missing vital status did not survive, all missing survived). ⁸⁴

For the secondary endpoint 1, missing data in the composite outcome of 28-day mortality or MOF incidence will be dealt with by using the method proposed by the authors of the validated Denver MOF score for scoring patients with missing data.^{80, 81}

Because the secondary endpoints 2, 3 and 4 (admission coagulopathy, acidosis and clot strength) are obtained at 30 minutes postinjury in all trauma activation patients, we anticipate very few missing data. The main and most complicated reason for missing data in these secondary endpoints is death before test was obtained. These data are clearly "missing not at random" (MNAR), as they are likely to represent the most injured patients and those more likely to have abnormal test values. This survivor-bias plagues emergency and trauma research and it is difficult to manage in the analysis period. ¹⁰⁹⁻¹¹¹ As recommended by the Panel on Handling Missing Data in Clinical Trials, missing data both due to death and related to death must be treated as a special case. ⁸⁴ We will proceed as follows for these analyses: 1) the primary analysis will focus on all patients with complete data; 2) the second analysis will focus on those who remained alive in either group; 3) a third approach will fold death occurring within 1-hour between ambulance arrival at scene into the two binary endpoints 2, 3 and 4 to form composite outcomes (admission coagulopathy or 1-hour death; admission acidosis or 1-hour death). For the continuous secondary endpoints 2, 3, and 4, we will limit the analyses to approaches 1 and 2 and as a third approach, multiple imputations will be used.

Missing data for the variables chosen to assess effectiveness of randomization are anticipated to be less than 5% given the mechanisms described above. For the variables MAR with >5% missing data, we will use the multiple imputation method. ^{81, 84} If the variable is MNAR, the missing indicator method, as proposed by [name] et al., which is equivalent to the inverse probability weighting method, will be employed. In brief, the variable is categorized in missing, normal value and abnormal value, using established cutoffs for normal and abnormal values.

Missing data procedures for exploratory analysis 1: By the very nature of the study, missing data for this outcome (24-hour mortality) as a binary outcome (death yes or no) is likely to be null; while missing data for time from injury to death within 24 hours can be missing, which will be censored in the above-described survival analysis.

I. Trial assessment

- 1. Assessing Phase 2 trial results for promising benefits of the therapy: Because the trial has low power for the primary endpoint and some of the secondary endpoints, it is unlikely that we can detect a statistical significant difference. Thus, it is important to pre-determine the findings that we believe will indicate promising results that must be further investigated in larger Phase 3 trials. We will specifically look at the following measures to declare that the therapy is promising:
 - a. Statistical significant difference in primary endpoint or secondary endpoints
 - b. Strong, yet not statistically significant association (e.g., p-value = 0.10 to 0.05) with improved primary and secondary endpoints. The direction

of the association must indicate therapy benefit in ALL primary and secondary endpoints. Associations indicating harm will be reviewed by the DSMB for possible early termination.

c. Exploratory analyses of variables with supporting evidence for association with improved patient outcomes with statistically significant results (respecting the boundaries determined by the interim analyses methods, and adjusted for multiple comparisons as detailed in the description of the exploratory analyses).

The DSMB will also be in charge to making recommendations regarding the promising nature of the therapy and whether Phase 3 trials are warranted.

2. Interrupting the trial early:

The DSMB will be responsible for making a recommendation for early stopping of the trial. The DSMB will be asked to address early termination during each and every time they are activated, as described in the DSMB roles and responsibilities. In brief, the DSMB will be activated in case of a unanticipated problem, or during the interim analyses. Drs. [name] and [name] will prepare the materials for DSMB review containing:

- a. blinded results (experimental and control groups will be referred as A and B) of effectiveness of randomization, primary and secondary outcomes, as well as exploratory analyses (most especially the two subgroup analyses regarding blunt versus penetrating mechanism, presence of traumatic brain injury and Field SBP≤70mmHg versus SBP 71-90mmHg), any potential adverse events, and missing data description (to include number missing and their characteristics regarding outcomes and covariates).
- b. predicted probabilities of all previous events and outcomes based on the Denver MOF database, the ROC trial, the National Trauma Data Bank and the Trauma registry: these statistics will assist the DSMB in determining harm based on larger numbers than those provided by the comparisons between control and experimental groups
- c. graphs containing the statistical scores, interim analyses boundaries and prediction of future statistical scores based on observed data.
- d. pertinent studies published since the initiation of the trial.
- e. any feedback received from community members, enrolled patients, paramedics, research coordinators and attending health care providers.

Based on the above elements, the DSMB will make a recommendation on early termination of the trial.

J. Paramedic training and ambulance equipment

 Paramedics will be trained utilizing a PowerPoint presentation that emphasizes the protocol, study background, inclusion-exclusion criteria and transfusion reactions. All trainees will have ample opportunity to ask questions and offer comments. Commencement of study enrollment will begin only after training is concluded. Paramedics authorized to perform study related procedures will be required to not only have completed and documented this mandatory training, but must provide certification of their credentials, prior to study initiation. All documentation will be reviewed and stored by the study coordinator. In addition, paramedics hired after this training has been completed will be required to review study training material and will be guided by veteran paramedics as well as the previously mentioned study staff. Study staff will meet with the trainees specifically to discuss the study and answer any questions.

- 2. As requested by the Jehovah's Witness Hospital Liaison (JWHL) Committee during the Community Consultation, the JWHL Committee will have the opportunity to educate and train the paramedics how to seek Jehovah's Witnesses.
- 3. For the study, all the DHMC paramedic ambulances will be equipped with validated coolers, (See Section IV.L.1 Dry Ice Plasma Storage Box) to store the 2 units of AB-FP24. The Thermal Isolation Chamber (TIC) panels will be exchanged every 48 hours and the AB-FP24, if not used, will be replaced every 11.5 months. According to the 28th Edition of the AABB Standards for Blood Banks and Transfusion Services, plasma frozen within 24 hours of phlebotomy expires at 12 months from collection. (See Appendix 12) Type AB plasma is a valuable resource that we do not want to waste or discard unless it is expired by the AABB standards. To be conservative, we will replace AB-FP24 at 11.5 months from collection. This method was deemed to be the most cost effective and logistically feasible in the ambulances. When the frozen AB-FP24 is needed, it will be rapidly thawed in a FDA approved dry warming device called Plasmatherm powered by a 12V to 120V AC inverter (see section IV.L.2 Plasmatherm).
- 4. The AB-FP24 will be infused once ready with the standard Y-set with blood transfusion filter (170-260 micron). If IV access has been obtained and the AB-FP24 is not ready to be infused, fluid resuscitation will not be withheld and crystalloid fluid will be infused until the AB-FP24 is thawed. This will minimize the possibility that subjects in the study group will receive inferior care if the AB-FP24 is not ready for infusion.
- **5.** Paramedics will briefly look for necklace ID or bracelet. If the patient has any of these, he/she will not be enrolled.
- 6. If the patient has a durable power of attorney that reports Jehovah's Witnesses or no blood products, regardless if fractions are accepted, we will not enroll the patient in the study. The degree that fractions will be accepted varies among members of the Jehovah's Witnesses congregation. Thus to be conservative and minimize the chance of enrolling patients that do not accept plasma fractions, we will not enroll these patients.
- 7. If a family member is present at the scene and not in shock or severely injured, easily accessible to paramedics, and the patient is not in imminent danger of death, the paramedics will state "We are enrolling him/her in a research study where we are giving a blood product. We don't have time to explain the study at this time. Is this okay?" The paramedics will not look for family members among a crowd of bystanders given the acute setting and the importance of transporting

the patient to the hospital as soon as possible. Paramedics cannot assess competency of family members in this time-sensitive setting; thus family members that are not in shock or severely injured will be assumed to be competent.

- **8.** It will be assumed that patients will not be competent to give an assent since by nature of the eligibility criteria, the patient will be in severe shock.
- 9. If the patient will not be transported to Denver Health, he/she will not be enrolled. If the patient is enrolled, but due to unforeseen circumstances (such as impending airway), must be transported to a nearby facility that is not Denver Health, then the patient will be unenrolled. If possible, every effort will be made to contact the family and follow the patient for any adverse effects. The consent form will be used to verify that the patient (or family) was informed.

K. Procedures involving plasma

- 1. Procedure for thawing frozen AB-FP24: AB-FP24 will be thawed in the Plasmatherm (see section IV.L.2) and in accordance to the instructions accompanying the product and as approved by the FDA.
- **Plasma is thawed but not transfused:** If the AB-FP24 is thawed but not transfused for unforeseen reasons, such as discovery of Jehovah's Witnesses, then the unit(s) will be discarded or used for research purposes. It will not be transfused into humans.
- 2. Procedure for Issuing 2 units of AB-FP24: Bonfils Blood Center will be providing the AB plasma for the study.. This is modified from the DHMC policy for Blood Transfusions to be applicable to this study.
 - a. AB-FP24 will be administered through the standard Y-set with blood transfusion filter (170-260 micron).
 - b. Vital signs are required before the transfusion of all components and again after 15 minutes and at the completion of the transfusion. Transfusion rate will be compatible with the patient's condition. The patient will be monitored closely during the entire transfusion. The documented start and stop times are directly related to the actual transfusion of the component. Paramedics will document vital signs and start times in the field. Study coordinators will assume responsibility of additional vital signs and stopping time of the AB-FP24.
 - c. The patient medical record shall include the following:
 - **1.** Name of the components transfused
 - 2. Donor identification number of components
 - 3. Date and time of transfusion (Start and Stop time)
 - **4.** Pre and post transfusion vital signs
 - **5.** The volume transfused
 - **6.** The transfusionist's name (paramedic)
 - 7. Documentation of related adverse events
- **3. Rescue procedure for transfusion reactions:** This is modified from the DHMC policy for Blood Transfusions to be applicable for this study.

- a. Careful observation throughout the transfusion allows for early detection of adverse reactions and optimal treatment, if necessary. All reactions should be handled initially as possible hemolytic reactions and the transfusion must be stopped. Any adverse events associated with the transfusion of blood or blood components should be documented in the patient's Medical Record and reported to the Blood Bank.
- b. The most common clinical events accompanying or announcing transfusion reactions are, in order of decreasing frequency:
 - 1. Fever, with or without chills
 - 2. Skin symptoms, hives and/or itching or rash
 - 3. Chest pain
 - 4. Hypotension
 - 5. Nausea
 - 6. Flushing
 - 7. Respiratory Distress (wheezing, coughing or dyspnea)
 - 8. Bleeding at infusion site
 - 9. Hemoglobinuria
 - 10. Circulatory overload
 - 11. Anaphylaxis
- c. If an adverse reaction is suspected, follow the procedure below:
 - 1. Stop the transfusion
 - 2. Maintain IV access with Normal Saline and change the tubing.
 - 3. Notify the patient's physician upon arrival to the ED and initiate immediate treatment as ordered.
 - 4. For all other blood products involved in a reaction, the transfusion shall be stopped and a Transfusion Reaction Investigation (F20-251) shall be initiated. This form can be obtained from the Blood Bank.
 - 5. Notify the Blood Bank [contact] of the suspected transfusion reaction.
 - 6. Collect a sample drawn from the patient as soon after the reaction was detected. Send a 6 mLs pink top tube, labeled with a new Blood Bank armband to the Blood Bank along with the unused blood, blood bag with attached hard back copy of the transfusion tag, the IV tubing used and the top 2 copies of the Transfusion Reaction Investigation 3 part form. The back copy of the Transfusion Reaction Investigation form should remain in the patient's chart as the initial report. A post transfusion reaction Urinalysis with Microscopic may also be ordered by the patient's physician.
 - 7. The Blood Bank will complete the Transfusion Reaction initial report and notify the caregiver of the critical results. Pathology

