- h. **Sample size and Power calculations:** This is a Phase 2 trial, powered to detect differences in this outcome as follows:

Power calculations: Admission Lactate

Assumptions 1: 80% power, 95% confidence, 2-tailed test, 3 equally spaced data analyses (2 interim, 1 final), using the O'Brien-Fleming method; control group mean admission lactate=2.0 mmol/L and standard deviation (SD) =2.0 (based on $^{67, 81, 91}$)

		(-)		- /					
Power	N1	N2	Alpha	Beta	Mean 1	Mean 2	SD	Difference	Attrition Rate
0.800000	60	60	0.050000	0.200000	2.00	0.97	2.00	1.03	20%
0.800000	68	68	0.050000	0.200000	2.00	1.03	2.00	0.97	10%
0.800000	75	75	0.050000	0.200000	2.00	1.08	2.00	0.92	0

Sample sizes of 60 and 60 achieve 80% power to detect a difference of 1.03 mmol/L between the two means, a clinically relevant difference, at a significance level (alpha) of 0.05 using a two-sided test. These results assume that 3 sequential tests are made using the O'Brien-Fleming spending function to determine the test boundaries.

Boundaries (Bndry) for data looks

Details when	n Spending = O'Bi	ien-Fleming,	N1 = 60, N2 =	=60, S1 = 2.00,	S2 = 2.00, Di	ff = 1.03	
	Lower	Upper	Nominal	Inc	Total	Inc	Total
Look	Bndry	Bndry	Alpha	Alpha	Alpha	Power	Power
1	-3.71030	3.71030	0.000207	0.000207	0.000207	0.018650	0.018650
2	-2.51142	2.51142	0.012025	0.011890	0.012097	0.398801	0.417451
3	-1.99302	1.99302	0.046259	0.037903	0.050000	0.382549	0.800000

Details when Spending = O'Brien-Fleming, N1 = 68, N2 = 68, S1 = 2.00, S2 = 2.00, Diff = 0.97

^{§§} Although the hypothesis is worded as "higher", all tests will be two-tailed to control for differences in either direction (higher or lower than the other group).

	Lower	Upper	Nominal	Inc	Total	Inc	Total
Look	Bndry	Bndry	Alpha	Alpha	Alpha	Power	Power
1	-3.71030	3.71030	0.000207	0.000207	0.000207	0.018650	0.018650
2	-2.51142	2.51142	0.012025	0.011890	0.012097	0.398801	0.417451
3	-1.99302	1.99302	0.046259	0.037903	0.050000	0.382549	0.800000
	T	II	NT 1	=75, S1 = 2.00,	T. 4.1		T.4.1
Look	Lower	Upper	Nominal	Inc	Total	Inc	Total Bower
Look	Bndry	Bndry	Alpha	Inc Alpha	Alpha	Inc Power	Power
Look 1		11		Inc		Inc	
Look 1 2	Bndry	Bndry	Alpha	Inc Alpha	Alpha	Inc Power	Power

Addendum November 16, 2016

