Based on the interim analyses, a proposed new sample size is: with 80% power, 95% confidence and assuming mean admission lactate=5 mg/dL with standard deviation of 2 in the control group (based on the second interim analyses data), with 5 interim analyses (4 interim and 1 final, of which 3 already occurred), we will require 112 patients in each group (assuming the attrition rate observed in this RCT of 12%) to detect a difference of 1 mg/dL between the two mean lactates. This results in a total of 224, which corresponds to an increase of 74 patients over the current sample size of 150 patients.

G. Exploratory analyses

- Exploratory analysis 1: 24-hour mortality Based on the control arm of the recent ROC trial⁶⁷ and our trauma registry data, the control group 24-hours mortality is estimated to be between 19% and 26%.
 - a. **Definition:** 24-hours mortality is defined as death within 24 hours post injury (death of any cause). Research coordinators will verify the vital status of all patients 24 hours postinjury and determine the time of death in relationship to injury.
 - b. **Hypothesis:** 24-hour mortality will be significantly higher^{***} in control patients compared to experimental group patients.
 - c. Statistical test: Logistic regression will be used to compare the 24-hour mortality in the two groups. Statistical significance will be evaluated at each interim analyses for the primary outcomes and p-values, as well as 95% and 99% confidence intervals will be reported to the DSMB for analyses. If adjustment for pre-defined confounders is needed, we will use the above-defined method for categorical, binary variables. Time from injury to death will be evaluated using the Kaplan Meyer curves, which will be compared using SAS PROC LIFETEST. We will use the Wilcoxon test (which places more weight on shorter survival times) and the log-rank test (which privileges longer survival times). SAS PROC LIFETEST also constructs statistics to test for

^{***} Although the hypothesis is worded as "lower", all tests will be two-tailed to control for differences in either direction (higher or lower than the other group).

association between covariates and the lifetime variable through rank tests for the association of survival time with covariates, if there are potential confounders detected using the above-described procedures.

2. Pre-planned subgroup analyses:

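### The November 2016 addendum puts admission lactate in mg/dL where the protocol planned in mmol/L, and its printed inputs give about 94% to 96% power, not 80%

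*Combined protocol and SAP*

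**What the plan says.** Section IV.F.4 (admission acidosis) has two power statements for lactate.

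- **Power table, Admission Lactate.** It assumes "control group mean admission lactate=2.0 mmol/L" and SD 2.0, a two-sided test and three equally spaced O'Brien-Fleming analyses. It lists 80% power for differences of 1.03, 0.97 and 0.92 with 60, 68 and 75 per group, at attrition of 20%, 10% and 0%. The text gives the 1.03 in mmol/L and calls it clinically relevant.
- **Addendum of November 16, 2016, directly after it.** For the same endpoint and the same 80% power it works from "assuming mean admission lactate=5 mg/dL with standard deviation of 2 in the control group" and sizes the trial "to detect a difference of 1 mg/dL between the two mean lactates". It states "we will require 112 patients in each group (assuming the attrition rate observed in this RCT of 12" per cent), and adds: "This results in a total of 224, which corresponds to an increase of 74 patients over the current sample size of 150 patients". The number of looks becomes five.

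The addendum neither converts between the two units nor explains the change.

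**The concern.** Two separate things do not fit.

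**Unit.** Taking the molar mass of lactate as about 90 g/mol (an assumption; the documents give no conversion), 1 mmol/L is about 9 mg/dL. Read literally, the addendum's control mean is then 5/9 ≈ 0.56 mmol/L, roughly a quarter of the 2.0 mmol/L planned. Its difference is 1/9 ≈ 0.11 mmol/L, about a ninth of the 1.03 called clinically relevant. Base deficit, the other marker of the same endpoint, moves the opposite way: the addendum's table in section IV.E shows 11.2 and 9.2 mEq/L against 5.15 anticipated.

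**Power.** The table already gives 80% power for a difference of 1.03 with SD 2.0 at 60 per group. The addendum asks for 112 per group for almost the same difference and the same SD.

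At stake is whether a reader can tell which lactate effect the enlarged trial was powered to detect. Section IV.I lists the secondary endpoints among the criteria for calling the therapy promising, so the planning statement should be reproducible.

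**Working it through.** **Inputs.** Difference 1, SD 2, 112 per group, 12% attrition and five looks come from the lactate addendum. The test is two-sided: the footnote to the lactate hypothesis says "all tests will be two-tailed to control for differences in either direction". The boundaries are those printed for five looks in the section IV.E addendum: 4.87688, 3.35695, 2.68026, 2.28979, 2.03100 at information times 0.2 to 1.0.

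**Method.** With n analysed per group, the drift at full information is θ = difference / (SD × √(2/n)). The look statistics are normal with means θ√t and correlations √(s/t) between looks at times s < t. Power is the probability that any look crosses its boundary, found by simulation. Under no effect the five-look boundaries give 0.0500, as they should.

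**Reproducing the plan's own figures**

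| Source | n per group | Difference / SD | θ | Power |
|---|---|---|---|---|
| Lactate table, 3 looks | 60 | 1.03 / 2.0 | 2.82 | 80.0% |
| Lactate table, 3 looks | 68 | 0.97 / 2.0 | 2.83 | 80.2% |
| Lactate table, 3 looks | 75 | 0.92 / 2.0 | 2.82 | 79.9% |
| INR addendum, 5 looks | 112 | 0.19 / 0.5 | 2.84 | 80.2% |

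The method recovers all three rows of the lactate table. It also recovers the INR addendum, if 112 is the number analysed.

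**The lactate addendum, 5 looks**

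- All 112 analysed: θ = 1 / (2 × √(2/112)) = 3.74, power **95.9%**. A fixed design gives Φ(3.74 − 1.96) = 96.3%, and a t test 96.1%.
- 12% lost: 112 × 0.88 = 98.56 analysed, θ = 3.51, power **93.5%**. The fixed-design figure is 93.8% to 94.0% for 98 to 99 analysed.
- A one-sided test gives still higher power, so sidedness does not explain the stated 80%.

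**What 80% power would need.** The five-look drift for 80% power is 2.837.

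- Sample size for difference 1, SD 2: n = 2 × (2.837 × 2 / 1)² = 64.4, so 65 analysed, and 65 / 0.88 = 73.9, so 74 enrolled per group.
- Detectable difference with SD 2: 2.837 × 2 × √(2/112) = 0.76 with 112 analysed, or 0.81 with 98.56.
- SD at which a difference of 1 has 80% power: 1 / (2.837 × √(2/112)) = 2.64 with 112 analysed, or 2.47 with 98.56.

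**Check without simulation.** Scaling the table's first row from 1.03 to 1 gives 60 × 1.03² = 63.7 per group. Going from three looks to five moves this only to about 65, so the extra looks cannot account for 112.

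The two parts are independent. If mean, SD and difference share one unit, relabelling that unit leaves power unchanged.

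**The case against.** **Rounding is a plausible cause.** The addendum does appear to round: group A base deficit is 11.2 in the section IV.E table and 11 in the base deficit addendum, and TEG G is 7.3 and then 7. The detectable lactate differences of 0.76 and 0.81 would both print as 1. An SD of about 2.47 would print as 2 and give 80% power for a difference of 1 after attrition. This stands as a possibility, and it is why the fix begins with a check. The documents do not say that these figures were rounded, and as printed the statement cannot be reproduced.

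**The 112 is a common number.** The same wording appears for the primary endpoint and for the other secondary endpoints, so for lactate it can be read as the difference detectable at a fixed size. That softens the word require. It does not rescue the figure, because at that size the difference detectable with 80% power is 0.76 to 0.81 on the printed SD.

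**Stronger readings that the documents do not support.** A reader might infer that the enlargement to 224 is unfounded. The addendum also derives 112 per group from the primary endpoint, and nothing here tests that derivation. A reader might also fear a lactate target about nine times too small in the analysis. The plan compares mean lactate by linear regression, with no margin or threshold, so the unit in the power paragraph does not enter the test. Nor is mmol/L proven: the section IV.E table has no lactate row, and the text above it counts base deficit among signs of milder injury although the printed values are higher than anticipated.

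**Conclusion.** The point holds as a reporting error in two parts.

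1. The unit of one endpoint changes from mmol/L to mg/dL without explanation. mmol/L is the likely intention, given the printed base deficit values and an SD equal to the planned 2.0, but this needs confirmation.
2. On the printed inputs, power is about 96% with 112 analysed per group and about 94% after 12% attrition, against the stated 80%. About 65 analysed, or 74 enrolled, per group would give 80%.

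This rests on a common SD of 2 in both arms, equal allocation, five equally spaced looks and the boundaries printed for the primary endpoint. The plan does not settle whether 112 is enrolled or analysed: the addendum's wording builds in attrition, while its INR figures reproduce only with 112 analysed. Neither reading gives 80% for lactate.

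On these inputs the error is conservative: lactate has more power than stated, so no claim of adequate power fails. The total of 224 and the planned analysis are unaffected.

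**What to change.** Check the lactate unit, the control SD and the intended difference against the second interim report. Then correct the unit in the addendum (probably to mmol/L), say whether 112 is enrolled or analysed, and restate the figure.

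- **If SD 2 is confirmed**, suitable text, with the confirmed unit added, is: *112 enrolled per group (about 98 to 99 analysed after 12% attrition) gives about 94% power for a difference of 1.0, or 80% power for about 0.81; with 112 analysed, 96% and about 0.76.*
- **If the SD or the difference was rounded**, print the unrounded values so that the stated 80% can be reproduced.

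The cost is one look at an existing report and one corrected paragraph. Sample size, boundaries and analysis do not change.
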